8.5. Complete and on-going clinical experiences with study drug

Deferasirox is registered for the treatment of adult and pediatric patients with chronic transfusional iron overload.

Thousands of pediatric and adult patients aged 2 to 80 years were enrolled in randomized controlled trials evaluating the safety and efficacy of deferasirox in the treatment of transfusional iron overload. Thousands of patients have received deferasirox in prospective studies and on clinical indication since its release. More than 1500 MDS patients have been included in clinical studies, which included iron chelation with DFX. The studies showed deferasirox to effectively chelate iron in patients with transfusional iron overload as demonstrated by decreases of hepatic iron concentration and serum ferritin (51,66,67,72,73).

The efficiency of deferasirox DT in chelating iron appears to be constant at all doses ranging from 5 to 40 mg/kg/day (3.5 to 28 mg/kg/day for the FCT formulation) and is not affected by age, gender, baseline LIC or underlying anemia (69).

Deferasirox film coated table (DFX-FCT) has been recently registered for showing an improved safety profile particularly regarding gastro-intestinal side effect (71).

9. STUDY RATIONALE

The scientific rationale for this study is the evolving understanding that iron-induced tissue damage is not only a process of progressive bulking of organs through high-volumes iron deposition, but also a reactive iron species related “toxic” damage.

Iron mediated damage can occur prior reaching high iron storage thresholds derived from thalassemia major setting, free toxic iron species being already present when transferrin saturation $>60\text{-}70\%$ (25); therefore a timely early adoption of iron chelation may be of benefit before overt iron overload is seen.

Our hypothesis is that early and low dose DFX-FCT is better tolerated and is able to prevent iron accumulation and consequently tissue iron related damage, by consistently suppressing iron reactive oxygen species (NTBI and LPI).

If this hypothesis is confirmed this approach could contribute to an improvement of clinical practice of patients managements. Additionally this approach might also be a contribute in preventing future iron overloaded related complication, in this already frail and co-treated patient population.

10. STUDY OBJECTIVES

10.1. Primary objective

Balance iron burden in one-year treatment in early phase of transfusion requirement by low dose (3.5 mg/kg) DFX-FCT (prevention of iron overload) as demonstrated by MRI (R2) documented hepatic iron concentration.

10.2. Secondary objectives

- Descriptive –observational objective: Definition of iron overload (including serological markers and MRI definition of iron loading in different tissues: liver, pancreas), tissue reactive iron species and oxidative stress in MDS at beginning of transfusional history (descriptive, observational).
- On year evolution of iron overload serologic markers
- Presence and quantitative evolution of toxic serum iron forms (iron tissue reactive species) under low dose DFX therapy.
- Verify if regular suppression of the “free iron forms” prevent accumulation of tissue iron.
- Evaluate the overall safety of deferasirox FCT formulation in patients with lower risk MDS at the beginning of their transfusional history
- Leukemic transformation (progression to leukemia or higher rIPSS scores)
- Hemopoietic response
- Costs analysis

10.3. Exploratory

Study of biological cellular damage by iron toxicity before and during treatment

11. STUDY DESIGN

11.1. Overview of study design

[figure not shown]
This is an open label, single arm, phase II, study.

The study includes a screening period (in which patients eligibility will be assessed) followed by a 1-year treatment period during which monthly visits will take place to evaluate safety and efficacy parameters (total 16 visits + 1 screening visit).

Study treatment with low dose (3.5 mg/kg/day) DFX-FCT will be given to all enrolled patients at the beginning of their transfusional history

Dose activity will be monitored by regular NTBI /LPI suppression and by prevention of iron accumulation as demonstrated by hepatic iron concentration, comparing baseline versus end of study iron concentration. It has been clearly demonstrated that liver iron concentration is proportional to total body iron stores (LIC x 10.6 = total body iron store in mg/kg)(39)

A standard pre-transfusional Hemoglobin level will be indicated (Hb threshold for transfusion Hb 9 g/dl or 10 g/dl for patients with cardiac disease) to be maintained during the study year. Pre transfusional hemoglobin level and transfusions date and frequencies will be recorded. A transfusional ratio will be determined: number of units received in a predetermined period/ mean pre-transfusional Hb level

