Study design	
 • This is an open-label, single arm, phase II, study designed to look whether early intervention with low dose DFX improves clinical outcome of patients with MDS. • Efficacy of early - low dose DFX FCT to prevent iron accumulation regularly suppressing reactive oxygen species. • Safety of early low dose DFX FCT. • Exploratory: possibility to guide chelation therapy by NTBI/LPI. • One arm • Fixed dose • Blinding: Open • Structure: Single Group • Randomized: Non-randomized • A standard pre-transfusion Hemoglobin level will be indicated (Hb threshold for transfusion Hb 9 g/dl or 10 g/dl for patients with cardiac disease) to be maintained during the study year. Pre transfusion hemoglobin level and transfusions date and frequencies will be recorded. A transfusional ratio will be determined: number of units received in a predetermined period/ mean pre-transfusion Hb level 	
Duration of the study	Enrolment 1 year. Per protocol treatment: 1 year. Total duration 2 years	
Number of patients	60 (50 + 10 for 20% drop out rate)	
Population	Adult MDS patients (≥ 18 years). Very low, low and intermediate risk group by revised-IPSS. Regularly transfused patients with low PRBC transfusion burden (less than 2 units/months for 3 consecutive months) at beginning of their transfusion story (total number of PRBC units received 5-20). Patients should not meet the published criteria for transfusion dependency (2 PRBC units /month for three consecutive months).	
Inclusion criteria	
Study population:
 
 • Diagnosis: Adult Myelodysplastic Syndrome (≥ 18 years). • Revised IPSS: very low, low – intermediate. 	

	
 Having received 5-20 packed red blood cell units Serum ferritin ≥ 300 ng/ml Transferrin saturation $\geq 60\%$ Chelation naïve Capability to provide informed consent

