6. STUDY FLOW CHART

7. INTRODUCTION. AIM OF THE STUDY

Iron chelation therapy in MDS patients receiving transfusion therapy has been developed on the basis of the large experience in transfusion dependent Thalassemia. However Thalassemia is a different clinical scenario compared to MDS for several different reasons. This study protocol has been developed to focus the specific setting of elderly MDS patients, inside the registered indications. This protocol has been designed to look whether early intervention with low dose DFX improves clinical outcome of patients with MDS.

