	Hemopoietic response	Percentage of patients with hematologic improvements in term of erythroid response following IWG 2006 criteria. Time to reach transfusion dependence defined as > 2 PRBC units/months for 3 months for patients with pre-transfusional Hb < 9.0 g/dl (or <10 g/dl for patients with cardiac disease) or a total number of PRBC units received = 20 from baseline. Absolute reticulocytes count from baseline to every visit during the whole treatment period. Absolute values and evolution of serum transferrin receptor, GDF11, GDF 15 and erythroferrone from baseline to every visit during the whole treatment period. Evaluation of transfusional ratio: number of units received in a

		predetermined period/ Mean pre-transfusional Hb level. Compared with other studies on general population (study and FISIM-ETS registry). Patients receiving concurrent rHuEpo will not be considered for erythroid response
	Costs analysis	Cost and outcome with low dose in early chelation vs. chelation treatment in MDS patients with transfusional iron overload in accordance with either local or international guidelines
Exploratory objective and endpoint	Study of biological cellular damage by iron toxicity before and during treatment	MDA values during the study and relationship to NTBI and LPI values

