20. STATISTICAL CONSIDERATIONS

20.1. Study design

One year low dose (3,5 mg/kg/day DFX-FCT) in patients at the beginning of their transfusion history. Dose activity will be monitored by regular NTBI /LPI suppression and by prevention of iron accumulation (hepatic iron concentration and other tissue and serologic parameters) comparing baseline versus end of study iron concentration.

[figure not shown]
A standard pre-transfusional hemoglobin level will be indicated (Hb threshold for transfusion Hb 9 g/dl or 10 g/dl for patients with cardiac disease) to be maintained during the study year. Pre transfusional hemoglobin level and transfusions date and frequencies will be recorded. A transfusional ratio will be determined: number of units received in a predetermined period/ mean pre-transfusional Hb level.

Open label, single arm, fixed dose phase II study.

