Demographic and other baseline data (including disease characteristics and transfusion history, etc) will be summarized descriptively for the Safety analysis set by means of the statistics above mentioned. Summary tables will be provided about medical history coded by System Organ Class and Preferred Term of MedDRA dictionary.

Treatments (study treatment, concomitant therapies, compliance)

The descriptive analysis listed below will be reported for the safety analysis set.

Study drug

The duration of study drug exposure, as well as average prescribed doses, will be summarized. Any dose adjustments and reasons that led to the adjustments will be listed. The number and duration of dose interruptions will also be described.

Compliance

Compliance based on prescribed amount of study medication versus amount of medication taken based on dispensed and returned amount of study medication will be summarized.

Concomitant Therapies

Concomitant medications and significant non-drug therapies prior to and after the start of the study treatment will be coded by WHO Drug Reference List dictionary and frequencies will be calculated according to drug classes.

The primary objective is prevention of iron accumulation measured by (primary variable) Change of hepatic iron from baseline according to baseline hepatic iron level: Baseline versus end of study.

For patients with baseline LIC ≤ 5 mg/g dry weight (dw) ± 1.5 mg/g dw.

For patients with baseline LIC > 5 mg/g dw $\pm 20\%$ (by R2- MRI ; test performed in a 1.5 tesla MRI machine and analyzed following R2 method (75).

The corresponding secondary efficacy variable will be the absolute change in hepatic iron concentration EOS versus baseline.

Difference between baseline versus EOT will be measured as continuous variables and analyzed with parametric or non parametric statistical tests depending by normality of distribution.

Secondary endpoint:

Observational: demographics and other baseline characteristics will be study with descriptive statistics. Analysis will be done on FAS and PP.

As the same way secondary endpoints will be evaluated as continuous or nominal variables and analyzed accordingly with parametric or non parametric tests. Efficacy parameters analysis will be done on FAS and PP.

Final Safety parameters will be measured in full analyses set and in all patients who received at least one dose of study drug (safety set).

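### The primary liver iron analysis takes no account of transfused iron, so in a single arm it cannot separate a drug effect from low iron input

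*Combined protocol and SAP*

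**What the plan says.** **Design.** Section 20.1 describes an "Open label, single arm, fixed dose phase II study". There is no untreated comparator for LIC.

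**Primary analysis.** Section 20.3 sets the primary variable as the change in hepatic iron from baseline to end of study. The reference band is ±1.5 mg/g dry weight when baseline LIC is 5 or less, and ±20% when it is above 5. On method it says: "Difference between baseline versus EOT will be measured as continuous variables", with a parametric or non-parametric test depending on normality. It plans no covariate or stratum for iron received, no expected change without treatment, and no external LIC comparator.

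**Transfusion data.** Section 11.1 states that "Pre transfusional hemoglobin level and transfusions date and frequencies will be recorded". Section 17.2.2 uses them under hemopoietic response: "Evaluation of transfusional ratio: number of units received in a" set period, divided by mean pre-transfusion hemoglobin, and "Time to reach transfusion dependence defined as > 2 PRBC units/months for 3 months". The ratio is to be compared with other studies and a registry. Section 20.3 also summarises transfusion history at baseline.

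**Other inputs to hand.** Body weight is taken at every clinic visit (Sections 16.1 and 16.6). Section 11.1 gives the conversion: "liver iron concentration is proportional to total body iron stores (LIC x 10.6 = total body iron store in mg/kg").

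**Who enters.** The Synopsis describes patients with "low PRBC transfusion burden (less than 2 units/months for 3 consecutive months"), who have received 5-20 units in total.

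**The concern.** Whether iron build-up was prevented can be judged only against the iron that went in. A flat LIC after many units is evidence that something removed iron. A flat LIC after two or three units is what would be expected with no treatment. The planned comparison treats these two patients alike, and no control arm supplies the missing reference.

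The error can also run the other way. In a heavily transfused patient, a drug that removed half the incoming iron could still leave a rise well outside the band, and a real effect would look like failure.

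Two further features could tilt the result towards uninformative stability. Patients whose drug is suspended for low ferritin stay in the study (Section 15.1), so stability off drug also counts. The early-withdrawal visit lists no MRI (Section 16.4), so patients stopped for high transfusion burden may have no final LIC.

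**Working it through.** The plan gives no expected LIC change without treatment, so there is no figure of its own to reproduce. The check asks how many units fit inside the band if the drug does nothing.

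**Inputs from the documents**
- Conversion: body iron (mg/kg) = 10.6 × LIC (mg/g) (Sections 8.2 and 11.1)
- Bands: ±1.5 mg/g if baseline LIC is 5 or less, ±20% if above 5 (Section 20.3)
- Treatment period: 12 months (Section 11.3)

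**Assumptions not in the documents**
- Iron per unit: 200-250 mg
- Body weight: 70 kg, range 50-90 kg
- No net iron absorption or loss other than by transfusion

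**Step 1. The ±1.5 band in body iron.** 1.5 × 10.6 = 15.9 mg/kg.

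**Step 2. Units that fill it.** Units = 15.9 × weight / mg per unit.

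| Weight | Iron to fill the band | Units at 250 mg | Units at 200 mg |
|---|---|---|---|
| 50 kg | 795 mg | 3.2 | 4.0 |
| 70 kg | 1,113 mg | 4.5 | 5.6 |
| 90 kg | 1,431 mg | 5.7 | 7.2 |

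**Step 3. The ±20% band, at 70 kg.** Units = 0.20 × LIC × 10.6 × 70 / mg per unit.
- LIC just above 5: 1.0 × 742 / 250 to 1.0 × 742 / 200 = 3.0-3.7 units
- LIC 8: 1.6 × 742 / 250 to 1.6 × 742 / 200 = 4.7-5.9 units
- LIC 10: 2.0 × 742 / 250 to 2.0 × 742 / 200 = 5.9-7.4 units

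**Step 4. Expected rise without drug, at 70 kg.** Rise = units × mg per unit / (70 × 10.6).
- 3 units: 600/742 to 750/742 = 0.8-1.0 mg/g, inside the band
- 12 units: 2,400/742 to 3,000/742 = 3.2-4.0 mg/g, outside
- 24 units: 4,800/742 to 6,000/742 = 6.5-8.1 mg/g, far outside. Halving this rise would leave 3.2-4.0 mg/g, still outside.

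**Step 5. Can such patients be in the trial?** Entry needs 5-20 lifetime units and a current rate below 2 units a month, with no stated minimum rate. About 5 units in the year is therefore compatible with entry. The upper end is open: the 2-unit limit applies at entry, and the transfusion-based discontinuation rule in Section 15.1 starts only above 4 units a month over three months. The figure of 24 units (2 × 12) is an illustration, not a ceiling.

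**The case against.** **The test is on a continuous change.** Section 20.3 plans a test of the difference and states no test of the proportion in band. On the continuous scale, 5 units at 70 kg and 200 mg give a rise of 1,000/742 = 1.35 mg/g. If that were the mean rise and the SD of change were 2.7 or less (the documents give no SD), the standardised effect would be at least 0.5. The paired t test with 50 patients then has about 93% power. Light transfusion would show as a rise, not as stability. This stands in part: the problem is sharpest where results are read against the band. The continuous test still gives no reference for how large a rise the transfusions alone would produce.

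**The objective is net balance.** Section 10.1 asks whether iron burden is balanced over the year, and LIC change measures that directly. Serial NTBI and LPI, and their relation to liver iron (Sections 16.7 and 17.2.2), give indirect evidence on drug action. A reader might infer that the trial cannot answer its own question. The documents do not support that: the net result is measurable, and only its attribution to the drug is weak.

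**Transfusion data are analysed.** A reader might also infer that they are collected and left unused. Section 17.2.2 shows otherwise. The gap is confined to the LIC analysis. What is recorded is dates and frequencies, and iron intake would have to be derived.

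**Very low intake may be uncommon.** The Synopsis describes regularly transfused patients, and a hemoglobin threshold is maintained through the year. The documents do not show how many patients would fall below about 5 units, so no share can be claimed.

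**Expected values are rough.** The 10.6 factor comes from thalassemia with a standard error of ±7.3 (Section 8.2). Read as mg/kg, that is 46% of the 15.9 mg/kg band (7.3/15.9). Section 8.1 also considers it likely that anaemia itself worsens iron load, and extra absorption would lower the unit thresholds. This is a good reason not to rest every claim of prevention on an observed-minus-expected figure. It is not a reason to leave intake out.

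**Conclusion.** The point holds for the primary LIC analysis. As planned, that analysis cannot distinguish a drug effect from low iron input. At 200-250 mg per unit and with no other net iron gain or loss, patients receiving up to about 4.5-5.6 units in the year at 70 kg (3.2-7.2 across 50-90 kg) could stay within ±1.5 mg/g untreated. At 24 units and 70 kg the untreated rise would be 6.5-8.1 mg/g, so stability there would be informative. The iron content, the weights and the zero-net-absorption condition are assumptions. The conversion factor is the plan's own.

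The primary analysis remains computable and meaningful as a measure of net balance. This is an inexpensive improvement that the sponsor should make for interpretation. It is not a fatal flaw.

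**What to change.** Keep the primary analysis and add to Section 20.3 a pre-specified supportive analysis:

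1. Derive each patient's on-study transfusion intake, as units and as units per kg.
2. Report LIC change by intake group, with groups fixed in advance, and the proportion in band by intake group for both baseline-LIC strata.
3. Regress LIC change on intake.
4. As a sensitivity analysis, report the group-level observed minus expected LIC change with a 95% CI, where expected = units × mg per unit / (weight × 10.6), at 200 and at 250 mg per unit. State the no-net-absorption assumption, the thalassemia origin of the 10.6 factor and its standard error of ±7.3.
5. State that any attribution of a stable LIC to the drug will be read alongside these results.

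The cost is about one paragraph and a few derived variables, with no new data collection. The downside is a little more analysis, and expected values that are only approximate.

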11.2. Number of patients

A total of 60 patients will be enrolled in the study: 50 +10 for a planned 20% drop out rate (drop out rate estimated on others DFX DT – MDS prospective studies).

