11.3. Duration of the study

Patients will be recruited over 12 months and followed for 1 year treatment phase. The anticipated study dates (start / end) are:

- Total accrual period (months/years): 12 months
- The duration of the treatment period is 12 months
- End of the study: last patient last visit.
- The Final Study Report will be provided after the end of the Study.

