15. REMOVAL OF SUBJECTS FROM TREATMENT AND/OR STUDY

15.1. Discontinuation from study treatment

Patients may voluntarily discontinue from the study treatment for any reason at any time.

If a patient decides to discontinue from the study treatment, the investigator should make a reasonable effort (e.g. telephone, e-mail, letter) to understand the reason for this decision and record this information in the patient's chart and on the appropriate CRF pages.

Patients may be considered withdrawn if they state an intention to withdraw, fail to return for visits / lost to follow-up for any other reason.

The investigator should discontinue study treatment for a given patient if, he/she believes that continuation would be detrimental to the patient's well-being.

Study treatment must be discontinued under the following circumstances:

- Death
- Adverse Events
- Abnormal laboratory value
- Pregnancy
- Unsatisfactory therapeutic effect
 - patients with evident inadequate chelation (Transfusion burden > 4 units/month over a three consecutive months period and > 1 PRBC unit/week and a total number of PRBC received >20) the protocol will be discontinued and the patient will be treated as clinically (by label) indicated
- Unwillingness to comply with study procedures/treatment as per protocol
- Discovery of patient ineligibility
- Intake of prohibited medications
- Protocol violation
- Consent withdrawal
- Lost to follow-up
- Administrative problems
- Premature termination of the study
- In patients with serum ferritin <300 ng/ml therapy will be suspended and the patient will remains in study, with the same transfusion (minimal Hb level 9 g/dl) and study criteria. Patients will restart treatment as soon as serum ferritin arise >300 ng/ml.

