20.2. Sample size calculation

Including 50 subjects in the study, we can reach almost 60% power to detect small effect size 0.30 (with p value of 0.05) whereas, we have almost 100% to detect moderate effect size of 0.50 (with p-value of 0.05). On the basis of previous experience, the low dosage, the early intervention and the FCT preparation a 20% drop out rate is expected (10 additional patients to be enrolled)

Methods:

The power test was performed by G power 3.1 software by using the t test Means: Difference between two dependent means (matched pairs).

As demonstrated by our sample size analyses, we have enough power to detect an effect size between 0.3 and 0.5 considering a potential error of 0.05, which is largely accepted from scientific community.

The effect size is calculated on a common scale by G-power program which allows to compare the effectiveness of different variables on the same outcome. In other words, quantifies the magnitude of the difference of a variable between two population groups.

To interpret the resulting number, most scientists use this general guide developed by Cohen:

- < 0.1 = trivial effect
- $0.1 - 0.3$ = small effect
- $0.3 - 0.5$ = moderate effect
- > 0.5 = large difference effect

20.3. Statistical method and data analyses.

Analysis population: the planned enrolment target is 50 patients (+ 20% drop out rate) for a total number of 60 patients.

Data from all centers participating in this study will be pooled for analyses.

Standard descriptive analyses will include:

- Frequencies and percentages for categorical data;
- n, mean, standard deviation, minimum, median, 25th and 75th percentiles and maximum for continuous data.

Whenever possible, the analysis will be performed by visit.

Analysis sets

Full Analysis Set (FAS): All enrolled patients.

Safety analysis set (SS): All enrolled patients who will have received at least one dose of study drug and have at least one post-baseline safety assessment. Note that an entry on the Adverse Event CRF of a statement that a patient had no adverse events constitutes a safety assessment.

Per Protocol analysis set (PP): All enrolled patients who will have received at least one dose of study drug without any major protocol violations and complete the treatment study phase or withdraw from the study due to unsatisfactory therapeutic effect.

Patient demographics/other baseline characteristics

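### The transfusional ratio has no defined period and takes no account of time under observation, so raw counts from patients who leave early would be too low

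*Combined protocol and SAP*

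**What the plan says.** Section 11.1 defines the ratio as "number of units received in a predetermined period/ mean pre-transfusional Hb level". The synopsis has the same definition ("number of units received in a predetermined period/ mean pre-transfusion Hb level" in its study design part, and again among the secondary endpoints), as do 14.5, 16.6, 17.2.2 and 20.1. None of these places gives the length or start of the period, and time under observation does not enter the formula.

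Other relevant statements:

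- **Data.** Section 11.1: "Pre transfusional hemoglobin level and transfusions date and frequencies will be recorded".
- **Follow-up.** Section 11.3: "The duration of the treatment period is 12 months".
- **Drop-out.** Section 11.2: "A total of 60 patients will be enrolled in the study: 50 +10 for a planned 20% drop out rate". Section 20.2 repeats it. Neither says when patients are expected to leave.
- **Discontinuation.** Section 15.1 lists unsatisfactory therapeutic effect, described through a high transfusion burden: "Transfusion burden > 4 units/month over a three consecutive months period", together with more than 1 unit per week and more than 20 units in total. For such patients the protocol is discontinued.
- **Analysis sets.** Section 20.3 analyses efficacy parameters on the FAS (all enrolled) and the PP set. The PP set takes completers and also patients who withdraw for unsatisfactory therapeutic effect.
- **Use.** Section 17.2.2 places the ratio under hemopoietic response and compares it with other studies and the sponsor's registry.

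**The concern.** A count of units depends on how long the patient was watched. If the period is the study year and a patient is observed for four months of it, the count covers a third of the period, but the formula treats it like a full one.

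Example over 12 months at a mean Hb of 9 g/dl:

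- A completer at 1.5 units/month scores 18/9 = 2.0.
- The same patient leaving at month 4 scores 6/9 = 0.67.
- A patient whose need rises to 5 units/month, stopped at month 4, scores at most 20/9 = 2.2. That is close to the stable completer, with more than three times the need.

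Per month of observation, the first two patients both score 1.5/9 = 0.17 and the third 5/9 = 0.56.

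Restricting to the PP set does not cure this, because that set keeps patients withdrawn for unsatisfactory effect, which 15.1 ties to high transfusion burden. In a single-arm trial the comparison with other studies and the registry is the only benchmark for this endpoint, and counts over unequal observation cannot be set against outside figures. An undefined period also leaves a choice that could be made after the data are seen.

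**Working it through.** **Inputs from the plan.** Treatment period 12 months (11.3); 50 + 10 = 60 patients (11.2, 20.2).

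**The plan's own figure.** 50 × (1 + 0.20) = 60 reproduces the target. Ten of 60 is 16.7% of those enrolled. If 20% of those enrolled were to leave, 50/(1 − 0.20) = 62.5, so 63 would be needed. Both readings are carried below: d = 10/60 and d = 0.20.

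**Inputs that the plan does not give (assumptions).**

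- f, the mean share of the period for which leavers are observed: range 0 to 1, with 0.5 for exits uniform over the period.
- k, the leavers' transfusion rate relative to stayers: 0.5 to 3.
- The window: 12 months, or the first 3 or 6 months.

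**Formula.** Take the stayers' full-period mean as 1. The true mean is (1 − d) + dk, and the raw-count mean is (1 − d) + dkf. With the same mean Hb in all patients, the proportional understatement is

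d(1 − f)k / (1 − d + dk).

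**12-month window, equal rates (k = 1).** The formula reduces to d(1 − f).

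| f | d = 10/60 | d = 0.20 |
|---|---|---|
| 0 (limit) | 16.7% | 20.0% |
| 0.25 | 12.5% | 15.0% |
| 0.5 | 8.3% | 10.0% |
| 0.75 | 4.2% | 5.0% |
| 1 (limit) | 0% | 0% |

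A constant drop-out hazard instead of uniform exits gives 8.6% and 10.4%. At equal rates, the understatement reaches 10% only if f is at most 1 − 0.10/d, that is 0.40 (d = 10/60) or 0.50 (d = 0.20).

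**Shorter window at the start (k = 1, exits uniform over 12 months).** For a window of L months the mean observed time of leavers is L − L²/24, so the share missed is L/24 and the understatement is d × L/24.

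- L = 3: 2.1% or 2.5%.
- L = 6: 4.2% or 5.0%.

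**Unequal rates (12-month window, f = 0.5).**

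| k | d = 10/60 | d = 0.20 |
|---|---|---|
| 0.5 | 4.5% | 5.6% |
| 2 | 14.3% | 16.7% |
| 3 | 18.7% | 21.4% |

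Dividing by observed time removes the exposure part of this error in every row.

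**The case against.** The strongest reply is that the definition already contains time: units in a fixed period are a valid rate for everyone who completes that period. The error arises only if the window is long enough for leavers to miss part of it and their partial counts are scored as complete. The plan says neither, and elsewhere it describes transfusion burden in three-month windows. This stands, and it makes the size conditional. It does not remove the gap, since the period is nowhere stated and no rule covers partial observation.

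A reader might infer that the understatement is at least 10%. The documents do not support a minimum. Ten percent is d/2 for 20% leaving, uniform exits, equal rates and a 12-month window; the plan's own 10 of 60 gives 8.3%, and the figure can be zero.

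A reader might also take 19% or 26% as likely. These follow if every leaver receives 3 or 5 units/month against 1.2 in completers, with 20% leaving uniformly. Nothing supports such rates for all leavers. Entry excludes patients at 2 units/month for three consecutive months. The 15.1 rule needs all three of its conditions, and its first cannot be met before three months on study.

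Other points that stand in part:

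- The plan sets no direction, threshold or test for the ratio, so it would be too strong to say that early exit will be read as benefit. Rising need is also captured by time to transfusion dependence.
- The plan does not say outright that recording of transfusions stops when a patient leaves, and patients suspended for low ferritin remain in the study. But 15.2 bars data collection after a patient declines to contribute further data, and no continued recording is described for other leavers.
- Recorded dates would allow repair at analysis. That shows that the fix is cheap, not that it is planned.

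**Conclusion.** The point holds as a defect of definition in a secondary endpoint: the period is not stated, and observed time is ignored although drop-out is planned and both efficacy sets can contain early leavers. Used as raw counts over the 12-month year, the ratio's mean would be understated by about 8-10% with uniform exits and equal rates. Across exit timings at equal rates the range is 0 to 17-20%. An initial 3- or 6-month window with uniform exits brings it to 2-5%; higher need among leavers raises it. Drop-out timing, leavers' transfusion rates and the window are all assumptions. Whatever the mean effect, values from patients with unequal follow-up are not comparable with each other or with outside data. The definition should be changed; the primary liver iron endpoint is untouched.

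**What to change.** In the synopsis (both places) and in 11.1, 14.5, 16.6, 17.2.2 and 20.1:

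1. State the window.
2. Define the ratio as units received per 28 days of observed time within the window, divided by mean pre-transfusional Hb. Observed time runs from first dose to the last day on which transfusions are recorded.
3. For the group, report total units over total observed patient-time, divided by mean pre-transfusional Hb, or fit a count model for units with log observed time as offset.
4. State that FAS patients who were never dosed contribute no observed time.
5. Put any registry or literature comparator on the same per-28-day basis.

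The cost is wording and one derived variable, with no new visits or data. Individual rates from short follow-up will be noisier, which the pooled rate or the offset handles. The change removes the exposure-time bias but not selective drop-out, so numbers leaving, reasons and times should be shown beside the ratio.
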